8.3 Protocol Deviations

A major deviations will be defined as participants enrolled and randomized but did not meet eligibility criteria during the course of the study. The number of participants in each protocol deviation category listed below will be summarized by analysis set and treatment group. Individual participants will appear in a listing.

Possible protocol deviations include the following categories:

- Participant entered study but did not meet criteria
- Participant developed withdrawal criteria but was not withdrawn
- Participant received excluded concomitant treatment
- Protocol procedure not performed per protocol
- Participant received incorrect treatment or incorrect dose
- Protocol procedure performed out of range
- Miscellaneous

8.4 Baseline Values

Baseline values are from Baseline Visits for all measures, except C-SSRS, AUDIT, DUDIT, resting blood pressure (BP), Body Mass Index (BMI). For C-SSRS, the initial screening visit will be conducted with the 'Lifetime' version of the measure. The Independent Rater Screening assessment of 'Since Last Visit' suicidal ideation and behavior will be used as 'Baseline.' For the

AUDIT and DUDIT measures and resting BP, BMI, results collected at Screening will be used as the Baseline value.

8.5 Participant Disposition and Dosing Summary

The All Enrolled Set will be included in the summary of participant disposition and accountability. The tabulation of number of participants in each treatment group and overall will be displayed for the Safety Set and in the *mITT* Set. The number and percent of participants who completed or discontinued the study will be displayed for each treatment group and overall together with reasons for early termination, where the percent is with respect to the total number of randomized participants in that treatment group. The timepoint of doses and total MDMA (mg) administered will be summarized by treatment group for the Safety and *mITT* Sets.

8.6 Demographics and Baseline Characteristics

Participant demographic data and Baseline characteristics will be summarized descriptively by treatment group and overall. The demographic data and baseline characteristics will be summarized for the *mITT* and Safety Sets.

8.7 Efficacy Analyses

For all primary, secondary, and exploratory endpoints descriptive statistics (n, mean, standard deviation, median, range, or counts and percentages where appropriate) will be provided by treatment group. Longitudinal CAPS-5 Total Severity Score and mean SDS item scores will be plotted across visits to characterize the onset of treatment effect.

8.7.1 Primary Efficacy Analyses

The *de jure* estimand of treatment efficacy will be used to estimate the causal effect of MDMA-assisted psychotherapy on PTSD symptom severity in the intended population of patients with PTSD from any cause (Estimand 1 in Table 4). All efficacy analyses will be based on the *mITT* analysis set. The primary treatment comparison will be made at a 2-sided, 0.0499 level of alpha. The primary estimator of effects of initially randomized treatments will be the difference between groups in mean change in CAPS-5 Total Severity Scores from Baseline to 18 weeks after randomization (Visit 19). Least squares means from a restricted maximum likelihood (REML)-based mixed model for repeated measures (MMRM) will be used to compare treatment groups at Visit 19. CAPS-5 data collected after treatment discontinuation will not be included in the *de jure* estimand. Missing data will not be imputed. The model is specified as follows: Let Y_{ij} be the change in the CAPS-5 score from the i th participant at the j th visit, $i = 1, \dots, n$ and $j = 1, 2, 3$, corresponding to post-baseline visits 8, 13, and 19, respectively. The treatment variable X_i is the randomized treatment of the i th participant. The variables T_1 and T_2 , are variables indicating if the data from that record are from visit 13, or 19, respectively. Covariates included in the MMRM model are the continuous baseline CAPS-5 Total Severity Score and the binary variable indicating dissociative subtype at baseline. Investigative site is included as a fixed effect. The regression model is specified as follows:

$$Y_{ij} = \alpha + \beta_1 X_i + \beta_{21} T_1 I(j=2) + \beta_{22} T_2 I(j=3) + \beta_{31} T_1 X_i I(j=2) + \beta_{32} T_2 X_i I(j=3) + \beta_4 \text{Baseline_CAPS}_i + \beta_5 \text{DS}_i + \phi \text{Site}_i + \varepsilon_{ij}$$

where $I(j=J)$ is the indicator function that equals 1 if $j=J$ and 0 otherwise. We assume that the Y_{ij} follow a Normal distribution with $\text{var}(Y_{ij}) = \sigma_{j2}$, and $\text{cov}(Y_{ij}, Y_{ij'}) = \sigma_{ij} = \sigma_{j'j}$ (unstructured correlation). The model above has been parameterized with reference cell coding where the coefficient estimate of β_1 corresponding to the treatment variable, X, captures the mean difference in the change from baseline CAPS-5 for MDMA vs. placebo. The coefficient estimates of β_{21} and β_{22} corresponding to the visit variables, T₁ and T₂ capture the difference in mean change in the CAPS-5 at visits 13 and 19 from the mean scores at visit 8, respectively. The coefficient estimates of β_{31} and β_{32} corresponding to the interaction of the treatment variable and the visit variable capture the incremental mean difference in the change in CAPS-5 for the MDMA group at visits 13 and 19 from visit 8 versus the placebo group. The coefficient estimate of β_4 captures the effect on the change in CAPS-5 post baseline corresponding to the baseline level of CAPS-5 score. The coefficient estimate of β_5 captures the effect on the change in CAPS-5 post baseline corresponding to dissociative subtype at baseline. The parameter ϕ captures the differences in mean change in CAPS-5 due to site differences. The following SAS code will implement this model and the statistical test for the MDMA vs. placebo comparison at Visit 19.

```
proc mixed;
  class ID X T Site DS;
  model CAPS = X T X*T Baseline_CAPS DS Site / s DDFM=SATTERTH ;
  repeated T / subject=ID type=un;
  estimate 'MDMA vs. Placebo at Visit 19' X 1 -1 X*T 0 0 1 0 0 -1 / e;
run;
```

where, the CAPS variable is the change from baseline in the CAPS-5 total severity score at each visit, the ID variable uniquely identifies the participant, Baseline_CAPS is the baseline CAPS-5 Total Severity Score for each participant, DS is the dummy variable indicating dissociative subtype at baseline, and Site indicates the clinical site where the participant was treated. There is a record for each visit for every participant. If the unstructured variance/covariance model assumption doesn't allow the REML algorithm to converge, a heterogeneous Toeplitz structure will be used. If the model doesn't converge under heterogeneous Toeplitz, the homogeneous Toeplitz structure will be used. If that fails to converge, the next variance/covariance attempted will be AR(1). In the event AR(1) structure fails to converge, the compound symmetry assumption will be used.

Table 4: Proposed Estimands and Key Attributes

Estimand	Hypothesis	Inference	Population	Endpoint	Use of data after early termination in analysis
1	de jure	Initially randomized treatment	mITT	Planned endpoint	Not included
2	de facto	Treatment Policy	mITT	Planned endpoint	Included

8.7.2 Supportive Analyses:

To support the need to provide information on treatment effectiveness in all randomized participants that could be expected in clinical practice, regardless of adherence to the 3-session

course of MDMA-assisted psychotherapy treatment, we propose a *de facto* estimand is included as an exploratory supportive analysis (Estimand 2 in [Table 4](#)).

The *de facto* estimand will include all available CAPS-5 outcome data from all participants in the mITT set regardless of adherence to the treatment, including CAPS-5 data collected after treatment discontinuation in case of early termination. This will be estimated in the mITT set by a statistical comparison between treatment groups using the MMRM model with a weighted least squares estimate of the change in CAPS-5 scores from baseline to 18 weeks after randomization across all the post treatment CAPS-5 measures. The sponsor expects no more than 5% of the participants will discontinue treatment after the first experimental session and CAPS-5 outcome assessment, due to the highly-controlled treatment setting which is analogous to residential or in-patient treatment settings. Additionally, some participants may choose to discontinue after the first experimental session because of strong and early positive response. These participants are treatment successes and should not be modeled as treatment failures. Using the least squares estimate of the mean reduction in CAPS-5 scores across all treatment sessions will capture these early successes in the *de facto* estimand. It can be argued that because all participants in the study will have continued data collection and all observed post-treatment CAPS-5 scores included in the *de facto* estimand that there is no missing data in this analysis. Thus the *de facto* estimand will support the primary *de jure* estimand.

1. The choice of primary estimand will be tested with a supportive analysis including a different estimand:
 - a. To determine *de facto* effectiveness by comparing MDMA-assisted psychotherapy to identical psychotherapy with inactive placebo for PTSD, as measured by the estimand of change in CAPS-5 Total Severity Score from Baseline after 18 weeks post-randomization, including all observed data after early termination.
2. The effect of departures from choices and assumptions made for the primary analysis will be tested as sensitivity analyses for the primary estimand. No sensitivity analyses will be performed for the secondary efficacy endpoints. Details of the sensitivity analyses with multiple imputation will be provided in the Final SAP.
 - a. Distributional assumptions for the full data will be tested, if distribution found not to be normal, we will test a transformation of the data, such as the log transformation, to achieve normality.
 - b. If outlying or influential observations are found: (1) a log transformation will be applied to the full data and (2) outliers will be excluded
 - c. Effect of covariates will be tested by conducting the primary analysis with and without: (1) dissociative subtype of PTSD based on CAPS-5 and (2) Baseline CAPS-5 Total Severity Score.
 - d. To examine the pre and post COVID-19 effect on the treatment effect the full model will be fitted with an additional binary dummy variable indicating whether the CAPS-5 measure was taken pre or post COVID-19. We chose to indicate the date of delineation between pre and post COVID-19 as March 11, 2020 – the day the World Health Organization declared COVID-19 a pandemic, and coincidentally, the data cutoff date of the Interim Analysis. The COVID-19 binary variable will be added to the full model specified for the primary analysis in a sensitivity analysis as a fixed effect along with an interaction term with the treatment variable. If the interaction term is not significant at the alpha 0.05 level it will be dropped from the model. The estimate of the COVID-19 dummy variable will be clinically interpreted and included in the interpretation and discussion of the primary efficacy results.
 - e. A concordance analysis will be executed to examine the effect of not completing all three (3) treatment sessions (treatment dropouts) on the treatment effect as measured by CAPS-5 [1]. The objective of the concordance analysis will be to address what

- the treatment effect would have been if all the treatment dropouts had completed the treatments and CAPS-5 measures. This will be compared to a worst-case scenario.
- f. To examine the robustness of the inferences to the MAR assumption, Jump to Reference and Copy Reference multiple imputation methods will be employed to ensure the most appropriate methodology is selected to test assumptions about missing data mechanism [2, 3]. Residual treatment effects are likely to carry over from observed periods during the study to the unobserved period after data collection ends for a dropout in some cases. Imputation method choice will depend on individual reasons for withdrawal (see Table 5). 1000 complete datasets will be generated; each of which will be analyzed using an ANCOVA model with effects for treatment arm, visit, and covariates. The final results will be obtained by combining the least squares (LS) means and LS mean differences from these 1000 analyses using standard multiple imputation methodology, and overall inference will be obtained by applying Rubin’s Rules on the estimates obtained from each imputed/complete data set [4].

Table 5: Inference of Treatment Effect for Missing Data from mITT Set Based on Reasons for Post-Randomization Withdrawal

Post-randomization Events	Available Data Post-Withdrawal	Treatment Assignment	Inference of Treatment Effect if Data is Missing (CAPS-5 Post Session 2 or 3)
Discontinue Study, Withdraw Consent	No data	MDMA	Assume treatment failure 
 • Jump to Reference Placebo arm
		Placebo	Assume treatment failure 
 • Copy Reference Placebo arm
Discontinue Intervention (or experiences long delay e.g., due to a pandemic) and does not receive Rescue Medication	Data collection continues whenever possible via remote visits	MDMA	Assume treatment success if post-treatment CAPS and reason supports treatment response 
 • Copy Reference MDMA arm Assume lack of tolerability if post-treatment CAPS and reason for dropping out do not support treatment response 
 • Jump to Reference Placebo arm
		Placebo	Assume treatment failure 
 • Copy reference Placebo arm
Discontinue Intervention (or experiences long delay e.g., due to a pandemic) and receives Rescue Medication	Data collection continues whenever possible via remote visits	MDMA	Assume treatment success if reason supports treatment response 
 • Copy Reference MDMA arm Assume treatment failure if reason does not support treatment response 
 • Jump to Reference Placebo arm
		Placebo	Assume treatment failure 
 • Copy Reference Placebo arm
Death	No data	MDMA	Assume treatment success if post-treatment CAPS supports treatment response 
 • Copy Reference MDMA arm Assume lack of tolerability if post-treatment CAPS and reason for dropping out do not support treatment response 
 • Jump to Reference Placebo arm
		Placebo	Assume treatment failure 
 • Copy reference Placebo arm
Suicide	No data	MDMA	Assume treatment failure 
 • Jump to Reference Placebo arm

Post-randomization Events	Available Data Post-Withdrawal	Treatment Assignment	Inference of Treatment Effect if Data is Missing (CAPS-5 Post Session 2 or 3)
		Placebo	Assume treatment failure 
 • Copy Reference Placebo arm

In exploratory analyses, additional baseline covariates (age, gender, ethnicity, index trauma, complexity and severity of trauma, medication tapering, diagnosis of comorbid depression, diagnosis of comorbid Axis 2 diagnosis, adverse childhood experiences) may be assessed for inclusion in the model at a $p < 0.05$.

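### SAP 8.7.2 does not settle what exploratory Estimand 2 estimates: Table 4 and item 1a set the 18-week endpoint, one rationale sentence describes a mean over all sessions, and no contrast is given

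*SAP*

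**What the plan says.** SAP 8.7.1 fixes the primary (de jure) comparison at Visit 19 and leaves out CAPS-5 scores collected after treatment discontinuation. Its code ends in a single contrast, "estimate 'MDMA vs. Placebo at Visit 19". This is the only CAPS-5 contrast in the SAP.

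Estimand 2 is the de facto version, which keeps the scores after discontinuation. Section 8.7.2 says it "is included as an exploratory supportive analysis". Its target is described in four places:

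- Table 4 enters "Planned endpoint" for both estimands.
- Item 1a defines it "as measured by the estimand of change in CAPS-5 Total Severity Score from Baseline after 18 weeks post-randomization".
- The estimator sentence calls for a weighted least squares estimate of change "from baseline to 18 weeks after randomization across all the post treatment CAPS-5 measures". It does not define the weights.
- The rationale concerns participants who stop early because they have already responded: "These participants are treatment successes and should not be modeled as treatment failures". It then says: "Using the least squares estimate of the mean reduction in CAPS-5 scores across all treatment sessions will capture these early successes".

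Item 1 states the purpose: "The choice of primary estimand will be tested with a supportive analysis including a different estimand". The same section also argues that, because data collection continues for everyone, nothing is missing in this analysis.

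**The concern.** A contrast at Visit 19 is not a mean over sessions. Two programmers working from 8.7.2 could produce different estimates, both defensible, and the choice could be made after results are known.

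The analysis exists to show what happens to the treatment difference when scores after discontinuation are put back. For that, it should differ from the primary analysis in data inclusion and in nothing else. If it is run as a visit average, the time point moves as well, and a gap between the two results cannot be attributed to either change. Estimand 2 is the only planned between-group MMRM of CAPS-5 that uses the scores after discontinuation, so no second model separates the two effects.

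**Working it through.** **Inputs.** From SAP 7.0, on the CAPS-4 scale: mean changes for placebo 5.5, 12.8, 20.5 and for MDMA 17.2, 31.1, 37.4; subject-level variance 335; residual variance 280; rho 0.5; 47 per group; alpha 0.0499; conversion to CAPS-5 by ×20/34. From SAP 8.7.2: at most 5% expected to discontinue after the first session and its CAPS-5. Complete data are assumed throughout. CAPS-5 equivalents are in brackets.

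**1. Reproduce the plan's power.** Variance at the last visit is 335 + 280 = 615. SE of the difference = √(2 × 615/47) = 5.12 [3.01]. Expected z = 16.9/5.12 = 3.30. Power is 91.0% by the normal approximation and 90.5% by noncentral t, against 90% stated. Residual variance 280 alone would give 99.8%, so 615 is the right total.

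**2. The two targets.** Differences at Visits 8, 13 and 19:

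- 17.2 − 5.5 = 11.7
- 31.1 − 12.8 = 18.3
- 37.4 − 20.5 = 16.9

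Visit 19 target: 16.9 [9.94]. Equal-weight average: (11.7 + 18.3 + 16.9)/3 = 15.63 [9.20]. Shift: 15.63 − 16.9 = −1.27 [−0.75], about 7%.

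The estimator is called weighted without saying how. If that means precision weights with AR(1) residuals (assumption), the weights are 0.4, 0.2, 0.4 and the target is 0.4 × 11.7 + 0.2 × 18.3 + 0.4 × 16.9 = 15.10 [8.88].

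**3. Compare with the effect the analysis should reveal.** Suppose 5% of the MDMA arm reverts fully to the placebo mean (assumption). The Visit 19 difference falls by 0.05 × 16.9 = 0.85 [0.50]. Reversion by 1.27/16.9 = 7.5% would be needed to equal the averaging shift.

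**4. Compare with sampling error.** Against the Visit 19 SE, the shift is 1.27/5.12 = 0.25. For the other comparisons, 335 is kept as variance shared across visits and the residual correlation structure is an assumption.

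| | Equal residual correlation 0.5 | AR(1), 0.5 |
|---|---|---|
| Variance of the average | 335 + 280 × 2/3 = 521.7 | 335 + 280 × 5.5/9 = 506.1 |
| SE of the average difference | √(2 × 521.7/47) = 4.71 | √(2 × 506.1/47) = 4.64 |
| Expected z for the average | 15.63/4.71 = 3.32 | 15.63/4.64 = 3.37 |
| Variance of (Visit 19 − average) | 280 × 1/3 = 93.3 | 280 × 4/9 = 124.4 |
| SE of (Visit 19 − average) | √(2 × 93.3/47) = 1.99 | √(2 × 124.4/47) = 2.30 |
| Shift divided by that SE | 1.27/1.99 = 0.64 | 1.27/2.30 = 0.55 |

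**5. The missing-data sentence.** Protocol 5.3.4 ends follow-up for participants who withdraw consent, apart from one final CAPS-5 if they agree to it. SAP Table 5 lists no data after withdrawal for consent withdrawal, death and suicide. Neither fits the argument that nothing is missing.

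**The case against.** The strongest reply is that the defining statements agree. Table 4 and item 1a point to 18 weeks, the estimator sentence itself mentions 18 weeks, and its reference to the MMRM leads back to 8.7.1, where the only contrast is Visit 19. On that reading, the words about all post-treatment measures mean only that every score enters the fit. This is fair for the estimator sentence. It does not rescue the rationale sentence, which names a mean over sessions and relies on that averaging to credit early responders. The inconsistency stands, but it rests largely on one sentence.

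A second reply is that a visit average with stated weights is a legitimate exploratory target. That is true. The defect is that the SAP has not named one target. Visit 19 is recommended because Table 4 and item 1a already say it.

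A reader might infer more than the documents support:

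- *Averaging inflates the test.* Expected z is 3.30 at Visit 19 and 3.32 to 3.37 for the average, a negligible difference. A larger gap appears only if rho 0.5 is applied to the total variance of 615. The between-visit covariance would then be 307.5, below the 335 that SAP 7.0 lists as shared, which is incompatible with a residual correlation of 0.5.
- *Averaging is pointless because early terminators will all have a Visit 19 score.* Protocol 5.3.4 and SAP 8.2 keep them on the planned rater schedule. However, Protocol 8.4.2 and 8.4.3 call for final assessments immediately on withdrawal, and Table 5 promises continued collection only where possible. On-schedule scores are not assured.
- *The aim overclaims by referring to everyone randomized.* The analysis set is stated plainly as mITT in Table 4 and 8.7.2, so this is minor.

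**Conclusion.** The concern holds as a low-impact inconsistency in an exploratory analysis. SAP 8.7.2 supports two targets for Estimand 2 and supplies a contrast for neither.

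The equal-weight shift of 1.27 CAPS-4 points [0.75 CAPS-5] is small beside sampling error, but larger than the 0.85 points that full reversion by 5% of the MDMA arm would produce. The time-point change could therefore mask or mimic the effect of including data after discontinuation. These figures rest on the SAP's planning means, complete data, equal weights, and the assumed residual structures and reversion.

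It would be wrong to infer any threat to the trial's main conclusion. The primary model and contrast are fully specified, and primary alpha, power and result do not depend on Estimand 2. Confidence is medium, because the reading on which the Visit 19 contrast is silently reused is plausible for part of the text.

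**What to change.** Before database lock, amend SAP 8.7.2 as follows.

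1. Define Estimand 2 as the Visit 19 contrast of the 8.7.1 MMRM, using the existing ESTIMATE statement, fitted to all observed CAPS-5 data including scores after treatment discontinuation. Remove or reword the sentence about a mean over all treatment sessions.
2. If a visit average is also wanted, report it under its own name with stated weights, beside the same average on the de jure data, so that only data inclusion differs.
3. Delete or qualify the sentence arguing that nothing is missing.
4. As a minor, separate point, reconcile Protocol 8.4.2 and 8.4.3 (assessment immediately on withdrawal) with Protocol 5.3.4 and SAP 8.2 (planned schedule), and state which analysis visit an at-withdrawal CAPS-5 is assigned to.

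The cost is wording, since model and code already exist. Precision falls slightly: SE 5.12 at Visit 19 against 4.64 to 4.71 CAPS-4 points for the average. Early responders still count, through their Visit 19 score where there is one and otherwise through their earlier scores in the MMRM under missing at random.

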8.7.3 Key Secondary Efficacy Analyses

For the key secondary analysis of efficacy, the de jure estimand will be used to estimate the causal effect of MDMA-assisted psychotherapy on PTSD on the SDS in the intended population of patients with PTSD from any cause (Estimand 3 in Table 4). The SDS is a 3-item scale measuring the severity of disability in the domains of work, family life/home responsibilities and social/leisure activities. Each of these three domains is scored on a ten-point Likert scale, where a score of 0 is ‘not at all impaired’, 5 is ‘moderately impaired’ and 10 is ‘very severely impaired’. The summary measure used to analyze the treatment effect on SDS will be the mean of the 3 item responses at each visit. Any participant who did not work during the reporting period due to reasons related to PTSD will be scored as a 10 on item 1. In cases where participants did not work due to reasons unrelated to PTSD, the score for item 1 (work/school) will be imputed by averaging the scores of items 2 and 3. It is expected that no more than 5% of participants will have item 1 (work/school) imputed, based on prior studies of paroxetine with PTSD. To limit missing data and ensure standardized administration, the SDS will be administered in a clinician-rated format during the same visits as the CAPS-5 by the centralized Independent Rater Pool. The clinician-rated administration will be important in limiting misinterpretation of the Work/school Impairment item that could contribute to elevated rates of skipping out, which can also be completed in reference to school, unpaid or volunteer work, and may not immediately come to mind in a participant-reported format.

If item 1 of the SDS is imputed in more than 5% of the participants, multiple imputation methods will be explored as an additional sensitivity analyses. If more than 5% of Item 1 data is missing, the frequency of participants not working due to reasons unrelated to PTSD and related to PTSD will be tabulated for both overall and within each visit. Additionally, a sensitivity analysis will be conducted to explore the effect of the different distributions for average SDS depending on whether the respective checkboxes for item 1 are checked or not. Separate MMRM models for the two types of responses to item 1 will be run and the treatment effect will be the weighted average of the two groups with the weights calculated as the frequency of checked item 1’s.

A hierarchical testing strategy will be employed to control for type-I error. That is, the hypothesis for the Key Secondary Endpoint (SDS) will only be tested if the statistical test for the Primary Efficacy comparison rejects the null hypothesis. If the statistical test for the Primary Efficacy comparison does not reject the null hypothesis, the analysis of the Key Secondary Endpoint (SDS) will be exploratory. The treatment comparison will be made at a 2-sided, 0.0499 level of alpha. The key secondary estimator of effects of initially randomized treatments will be the difference between groups in mean change in the SDS summary measure from Baseline to 18 weeks after randomization (Visit 19). Least squares means from a restricted maximum likelihood (REML)-based mixed model for repeated measures (MMRM) will be used to compare treatment groups at Visit 19. SDS data collected after treatment discontinuation will not be included in the de jure estimand. Missing data will not be imputed and will be considered missing at random. The model is specified as follows: Let Y_{ij} be the change in the SDS summary measure from the i th

participant at the j th visit, $i = 1, \dots, n$ and $j = 1, 2, 3$, corresponding to post-baseline visits 8, 13, and 19, respectively. The treatment variable X_i is the randomized treatment of the i th participant. The variables T_1 and T_2 , are variables indicating if the data from that record are from visit 13, or 19, respectively. Covariates included in the MMRM model are the continuous baseline SDS summary measure and the binary variable indicating dissociative subtype at baseline. Investigative site is included as a fixed effect. The regression model is specified as follows:

$$Y_{ij} = \alpha + \beta_1 X_i + \beta_{21} T_1 I(j=2) + \beta_{22} T_2 I(j=3) + \beta_{31} T_1 X_i I(j=2) + \beta_{32} T_2 X_i I(j=3) + \beta_4 \text{Baseline_SDS}_i + \beta_5 \text{DS}_i + \phi \text{Site}_i + \epsilon_{ij},$$

where $I(j=J)$ is the indicator function that equals 1 if $j=J$ and 0 otherwise. We assume that the Y_{ij} follow a Normal distribution with $\text{var}(Y_{ij}) = \sigma_j^2$, and $\text{cov}(Y_{ij}, Y_{ij'}) = \sigma_{jj'} = \sigma_j^2 \rho_{jj'}$ (unstructured correlation). The model above has been parameterized with reference cell coding where the coefficient estimate of β_1 corresponding to the treatment variable, X , captures the mean difference in the change from baseline SDS measure for MDMA vs. placebo. The coefficient estimates of β_{21} and β_{22} corresponding to the visit variables, T_1 and T_2 capture the difference in mean change in the SDS summary measure at visits 13 and 19 from the mean scores at visit 8, respectively. The coefficient estimates of β_{31} and β_{32} corresponding to the interaction of the treatment variable and the visit variable capture the incremental mean difference in the change in the SDS summary measure for the MDMA group at visits 13 and 19 from visit 8 versus the placebo group. The coefficient estimate of β_4 captures the effect on the change in the SDS summary measure post baseline corresponding to the baseline level of the SDS summary measure. The coefficient estimate of β_5 captures the effect on the change in SDS summary measure post baseline corresponding to dissociative subtype at baseline. The parameter ϕ captures the differences in mean change in SDS summary measure due to site differences. The following SAS code will implement this model and the statistical test for the MDMA vs. placebo comparison at Visit 19.

[figure not shown]
```
proc mixed;
  class ID X T Site DS;
  model SDS = X T X*T Baseline_SDS DS Site / s DDFM=SATTERTH ;
  repeated T / subject=ID type=un;
  estimate 'MDMA vs. Placebo at Visit 19' X 1 -1 X*T 0 0 1 0 0 -1 / e;
run;
```

where, the SDS variable is the change from baseline in the SDS summary measure at each visit, the ID variable uniquely identifies the participant, Baseline_SDS is the baseline SDS summary measure for each participant, DS is the dummy variable indicating dissociative subtype at baseline, and Site indicates the clinical site where the participant was treated. In the data used to fit the model, there is a record for each visit for every participant. If the unstructured variance/covariance model assumption doesn't allow the REML algorithm to converge, a heterogeneous Toeplitz structure will be used. If the model doesn't converge under heterogeneous Toeplitz, the homogeneous Toeplitz structure will be used. If that fails to converge, the next variance/covariance attempted will be AR(1). In the event AR(1) structure fails to converge, the compound symmetry assumption will be used.

